8.8. Definition of End of Trial

The end of study is the date of the last study contact.

9. STUDY INTERVENTIONS

In each of the three studies, participants will be offered four one-hour sessions of individual therapy with a qualified clinical psychologist with expertise in dissociative difficulties. These will take place within the five-week intervention window, and will be held at an NHS or University of Birmingham site, or the participant's home, according to their preference.

Each intervention will target the putative maintenance mechanism of interest for that study (see below). In each study, the first session will also include socialisation to the therapy session format and psychoeducation about how the mechanism might relate to dissociative experiences. Sessions 1 to 3 will involve learning and practicing active change techniques, whilst the final session will focus on consolidation of new information, planning for the future, and managing the therapeutic ending.

Practice of techniques between sessions will be encouraged, and may be supported by additional between-session contact (e.g. text messages, telephone calls, or meetings to carry out behavioural experiments in a supported manner) with an assistant (graduate-level) psychologist where indicated.

This therapy will be provided in addition to usual care. The quality of the therapy will be checked by the independent rating of audio-recordings of sessions by the therapist's clinical supervisor. Audio-recording of therapy sessions is optional – permission will be sought from participants at each session, and verbal consent confirmed at the start of the recording. Each time, participants will be reminded that they may request the recording to stop and/or be deleted at any time. To enable reporting of treatment delivery and fidelity, details such as the date, duration, and key discussion topics of each session will be recorded by the therapist for each session. All missed or cancelled therapy appointments will be recorded.

As noted above (6. Objectives And Outcome Measures), one of the aims of the study is to understand which therapy materials may be most helpful for future treatment development. Therefore, the details below – particularly with respect to administration of patient-facing materials – are preliminary and subject to personalisation for each participant as appropriate. Full details of this personalisation will be recorded and reported.

9.1. Study 1 – Negative Cognitive Appraisals of Dissociative Experiences

The key therapeutic technique delivered in this intervention will be cognitive restructuring, drawn from classical cognitive-behavioural therapy (e.g.³⁴).

Participants will be supported to understand what cognitive appraisals are, learn to notice and record these using a cognitive appraisals log/diary, and then supported to use an extended log/diary to challenge and adjust any negative assumptions contained within these. The aim is for participants to become more aware of the automatic appraisals they are making of their dissociative experiences and replace these with more balanced judgements.

There is extensive evidence for the use of this technique across the full range of mental health presentations, particularly in depression and anxiety, but also in a dissociative diagnosis: depersonalisation disorder³⁵.

9.2. Study 2 – Perseverative Thinking (Rumination)

The key therapeutic techniques delivered in this intervention will be those used effectively in a four-session worry intervention for persecutory delusions³⁶.

Participants will be supported to consider their positive and negative beliefs about worry, identify their typical triggers for worry, and learn and practice problem-solving and worry-management techniques.

This therapy has been thoroughly tested in the context of psychosis³⁶⁻³⁸ and demonstrated to be effective in reducing worry, as well as the downstream effect of worry in this context: paranoia. It is therefore anticipated to have a similar effect in the context of dissociation.

9.3. Study 3 – Affect (Emotion) Intolerance

The key therapeutic techniques delivered in this study will be drawn from CBT and dialectical behavioural therapy (DBT).

Participants will be supported to explore their own beliefs about emotions (CBT) and learn why affect is necessary and adaptive for daily life (DBT). They will work with the therapist to identify their individual triggers for affect intolerance (CBT/DBT) and respond to these in the most relevant way,

including: learning and practicing DBT coping strategies; carrying out behaviour experiments to test their assumptions/beliefs (CBT); or carrying out cognitive restructuring to balance beliefs/appraisals (using the same techniques as in Section 10.1, *Study 1*; CBT).

These techniques have been used effectively in the treatment of emotion dysregulation and affect intolerance³⁹. They are therefore anticipated to have a similar effect in the context of dissociation.

10. SAFETY REPORTING

Adverse events are rare in these kinds of studies. Adverse events are likely to come to the attention of the assessor or therapist, but all medical notes will be systematically checked for serious adverse events following completion of the final assessment to ensure all adverse events are recorded. The responsible clinical team will be informed of any adverse event. The responses to an adverse event will be determined on a case-by-case basis. The University of Birmingham Quality Management System procedures for safety reporting will be followed.

10.1. Definition of Serious Adverse Events

A serious adverse event is any untoward medical occurrence that:

- results in death
- is life-threatening
- requires inpatient hospitalisation or prolongation of existing hospitalisation
- results in persistent or significant disability/incapacity

Other ‘important medical events’ may also be considered a serious adverse event when, based upon appropriate medical judgement, the event may jeopardise the participant and may require medical or surgical intervention to prevent one of the outcomes listed above.

Formal complaints regarding therapy or research procedures will also be recorded.

10.2. Reporting Procedures for Serious Adverse Events

All serious adverse events that come to our attention are reviewed by the study team. These include serious events which are:

- Related to the intervention/study procedure related or not;
- Anticipated and unanticipated serious events;

A serious adverse event (SAE) occurring to a participant should be reported to the REC that gave a favourable opinion of the study where in the opinion of the Chief Investigator the event was ‘related’ (resulted from administration of any of the research procedures) and ‘unexpected’ in relation to those procedures. Reports of related and unexpected SAEs should be submitted within 15 working days of the Chief Investigator becoming aware of the event, using the HRA report of serious adverse event form (see HRA website).

The study team will make an initial assessment of whether the SAE is potentially related to the study procedures or intervention and report to the regulatory authorities within the appropriate timescales.

10.3. Events exempt from immediate reporting as SAEs

Hospitalisation for a pre-existing physical health condition, including elective procedures planned prior to study entry, which has not worsened, does not constitute a serious adverse event.

11. DATA ANALYSIS

The statistical aspects of the project are summarised here, and will follow the procedures recommended for this study design⁴⁰.

11.1. Statistical Analysis

Given the design and sample size, analysis will be descriptive in nature and no hypothesis testing will be carried out. The three studies will be analysed separately according to the following analysis plan.

12.1.1 Quantitative data

First, patient outcome measures will be presented graphically, and visual and statistical analysis used to assess within- and between-phase data patterns, as per the recommendations for SCEDs⁴⁰.

- Within-phase analysis:
 - level (mean and standard deviation and/or median and interquartile range);
 - trend (visual analysis or whether datapoints are increasing / decreasing);
 - stability (whether 80-90% of datapoints fall within 15% of the mean or median⁴⁰).
- Between-phase analysis:
 - Immediacy of effect (visual analysis);
 - Consistency of data patterns (visual analysis; trend analysis);
 - Overlap between phases (nonoverlap statistics e.g. extended celeration line or two standard deviation band method; as appropriate⁴⁰).

The above information will be used to form a judgement as to whether the data indicates that the intervention is causing a change in outcome measure scores. If so, effect sizes (Tau-U⁴¹) will be calculated.

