8.5. Blinding and code-breaking

This study does not involve blinding. However, to incorporate a degree of impartiality, assessments will be carried out by a research assistant, not the therapist.

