11.5. The Level of Statistical Significance

This is not applicable: no significance testing will be undertaken given the small sample size and exploratory nature of the study.

11.6. Procedure for Accounting for Missing, Unused, and Spurious Data.

There will be no statistical methods applied for handling missing data as this approach is inconsistent with the single experimental case design. For each participant, phases with fewer than five datapoints will be omitted from analysis, since this is the minimum recommended for within-phase analyses⁴⁰.

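### Tau-U, the plan's only named effect size, is calculated only after a judgement from the same ratings that the intervention works, so the reported values are selected

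*Combined protocol and SAP*

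**What the plan says.** Section 11 says the analysis "will follow the procedures recommended for this study design", citing a published guideline. Section 11.1 makes it descriptive, without hypothesis testing, and adds: "The three studies will be analysed separately according to the following analysis plan".

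Section 12.1.1 then sets an order of work:

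1. Graphs and within-phase summaries: level, trend and stability.
2. Between-phase comparison: immediacy, consistency and overlap, the last by "nonoverlap statistics e.g. extended celeration line or two standard deviation band method", as appropriate.
3. All of this is used to "form a judgement as to whether the data indicates that the intervention is causing a change in outcome measure scores".
4. "If so, effect sizes (Tau-U⁴¹) will be calculated".

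Steps 1 and 2 are unconditional, subject to Section 11.6: "phases with fewer than five datapoints will be omitted from analysis". Step 4 depends on a positive answer at step 3. No other section provides Tau-U when the answer is negative. The only other mention of effect sizes, in the Background (Section 4), concerns earlier research.

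The document gives no numerical threshold for the judgement and no rule for combining its inputs. It does not say whether the judgement is made per participant, per outcome or per study. On blinding, Section 8.5 says: "This study does not involve blinding".

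**The concern.** The judgement and Tau-U use the same ratings. If Tau-U exists only when those ratings already look like a change, the cases where chance separated the phases are kept and the cases where chance brought them together are dropped. The reported values are then, in general, larger in absolute size than the values over all participants. A null or unclear result gets no effect size at all.

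If the judgement is made per study, the selection is between studies: a study reports Tau-U for all its evaluable participants or for none.

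Section 5 sets the primary objective as finding out whether a larger study is justified, and says the data may supply initial figures for sample-size calculations. A planner who used the reported Tau-U values for that purpose would start from a selected set. This consequence is conditional: Section 5 does not name Tau-U, and the phase means and SDs (or medians and IQRs) are available to everyone.

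**Working it through.** **The plan's own figures.** The plan states no expected Tau-U, SD, autocorrelation or threshold, so there is nothing to reproduce. The size can only be illustrated.

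**Inputs from the document**
- Four participants per study (Synopsis), with baselines of 1, 2, 3 and 4 weeks (Section 8.4) rated daily: nA = 7, 14, 21 and 28.
- Intervention window of five weeks, or 35 days (Section 6). Rating every other day (Sections 6, 8, 9.6.2 and Appendix B) gives nB = 18. Daily rating (Synopsis and the Section 5 table) gives nB = 35. Both were run.
- Two overlap methods named as examples (Section 12.1.1).

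**Assumptions**
- Normal AR(1) ratings with unit SD, autocorrelation 0, 0.3 or 0.5, and a true downward shift of 0, 0.3, 0.5, 0.8 or 1.2 SD.
- *Celeration rule*: split-middle line through A1, extended into B1. It passes if at least 14 of 18 (or 24 of 35) B1 ratings lie on one side. For 14 of 18 the two-sided binomial probability is 2 × (3060 + 816 + 153 + 18 + 1) / 2^18 = 8096 / 262144 = 0.031.
- *Two-SD rule*: two consecutive B1 ratings outside the A1 mean ± 2 SD, on either side.
- *Both*: the two rules pass in the same direction.
- *Study level*: at least 2, or at least 3, of 4 participants pass in the same direction.

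**Statistic.** Tau = (pairs with B > A minus pairs with B < A) / (nA × nB).

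**Check without selection.** For normal data with shift d, Tau is expected to be close to 2Φ(-d/√2) - 1. For d = 0.3, 0.5, 0.8 and 1.2 this gives -0.168, -0.276, -0.428 and -0.604. The simulated means over all participants are -0.17, -0.28, -0.43 and -0.60.

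**Main case: 0.5 SD, autocorrelation 0.3, nB = 18, 20,000 studies. Mean Tau over everyone: -0.28**

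| Rule | Per participant (pass) | At least 2 of 4 | At least 3 of 4 |
|---|---|---|---|
| Celeration line | -0.28 (75%) | -0.28 | -0.29 |
| Two-SD band | -0.43 (24%) | -0.36 (21% of studies) | -0.40 to -0.41 (3-4%) |
| Both agree | -0.47 (12%) | -0.38 (6-7%) | too few pass |

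The bias is the difference from -0.28: about 0.00 to 0.01 for the celeration line. For the two-SD band it is 0.43 - 0.28 = 0.15 per participant and 0.36 - 0.28 = 0.08 at 2 of 4. For both rules agreeing it is 0.47 - 0.28 = 0.19 per participant. Subtracting the A1 trend from Tau gives a similar picture in the same cell: all -0.28, celeration -0.29, two-SD -0.43, both -0.52 per participant.

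**Other true shifts, over autocorrelation 0 to 0.5 and both rating frequencies**

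| Shift | Everyone | Celeration, per participant | Two-SD, per participant | Two-SD, at least 2 of 4 |
|---|---|---|---|---|
| 0.3 SD | -0.17 | -0.17 | -0.23 to -0.30 | -0.21 to -0.26 |
| 0.8 SD | -0.43 | -0.43 | -0.51 to -0.56 | -0.45 to -0.48 |
| 1.2 SD | -0.60 | -0.60 to -0.61 | -0.65 to -0.69 | -0.61 to -0.62 |

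**No true effect (autocorrelation 0.3, nB = 18).** Mean absolute Tau rises from 0.20 to 0.21 (celeration, 74% pass) or about 0.32 (two-SD, 15% pass). The signed mean stays at zero because either direction counts as change.

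**Why the two rules differ.** The celeration rule selects little because it rejects little: over the settings run, 69 to 85% of participants pass it with no true effect.

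**The case against.** The strongest reply is that little depends on Tau-U. The analysis is descriptive, no test is planned, and Section 5 disclaims adequate power for its secondary, causal question. Graphs, level, trend, stability and overlap are given for everyone, and with four participants per study a missing Tau-U is plain to see. The plan nowhere averages Tau-U across studies. All of this stands, and it limits the harm to readers who rely on the Tau-U values.

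Second, Section 11.2 cites a convention of at least four demonstrations of change, obtained across the participants of a study, and Section 11.1 keeps the studies separate. That points towards a study-level judgement, where the bias is smaller: under the 2-of-4 rule, 0.00 to 0.05 at 0.8 SD and 0.00 to 0.02 at 1.2 SD. The reading is reasonable, but the convention belongs to the sample-size rationale and is not stated as the criterion in Section 12.1.1. A stricter study-level rule also selects more. Requiring all 4 of 4 in the main case gives about -0.30 to -0.31 for the celeration line (5% of studies pass) and about -0.45 for the two-SD band (under 0.3% pass, so imprecise).

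Third, the pass rules above are assumptions, and overlap is one of six inputs to the judgement. That is correct, and it is why no single size is claimed.

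Fourth, the cited guideline may supply criteria. It cannot be consulted here, but clearer criteria would not remove the protocol's own condition on calculating Tau-U. Lack of blinding is likewise not the cause: a blinded analyst applying this condition would also select.

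**Conclusion.** The concern holds. As written, the plan calculates its one named effect size only after a positive reading of the same data. That conclusion rests on the text and needs no simulation: a study judged negative would have no planned effect size, however small the bias elsewhere.

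Confidence in the size is low. Under the assumed rules the shift in mean Tau runs from essentially zero (celeration line) to about 0.19 (both methods agreeing, per participant, true shift 0.5 SD). It shrinks at study level as the true effect grows. The size under the judgement the analysts would actually make, which draws on all the listed information, is not known. No error rate is affected. This should be fixed because the remedy is simple, but it does not threaten the study.

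**What to change.** Replace the conditional sentence at the end of Section 12.1.1 with:

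> *Tau-U (A1 vs B1) will be calculated and reported for every participant with evaluable phases (at least five datapoints) and for both VAS outcomes, whatever the visual judgement.*

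The same sentence should name the Tau-U variant (with or without baseline-trend correction), which the plan leaves open. Any planning estimate that uses Tau-U should be based on all evaluable participants. Visual analysis can still come first; only the condition goes. No confidence interval is asked for. If one is added, the report should note that the standard interval ignores serial dependence.

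The cost is one sentence and a few more calculations, with no new data or visits. The reported effects may look less favourable.

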12.1.2 Qualitative data

Written and transcribed qualitative data arising from requests for feedback on the research process and therapy intervention (see Section 9.6.3, *Qualitative Feedback*) will be analysed using Thematic Analysis³². This analysis will be managed within qualitative analysis software. Quality guidelines³³ will be followed, including credibility checks and reflexive practice. This approach has been used before by the CI with a similar participant group⁶. Key themes arising from this analysis will be reported within the study results.

11.2. Sample Size Determination

The aim of SCED studies is to use repeated phases with and without the application of the experimental intervention to demonstrate that it is the intervention that is causing the observed effect. In essence, this allows the same participant to contribute both control and intervention data, increasing information about probable cause and effect in contexts where it may not be feasible to run a fully powered randomised controlled trial³¹. General convention suggests that demonstrating changes in the outcome measure after introducing or withdrawing the intervention must be done a minimum of four

times to imply a functional relationship between intervention and effect⁴⁰. Typically, this can be achieved by repeatedly introducing and withdrawing an intervention with the same participant. However, this method is less valid in clinical psychology, where carry-over effects are expected from the intervention, and repeating the intervention may not be practicable. Thus, the multiple-baseline design (MBD) across individuals allows the requisite number of transitions (from intervention to ‘no intervention’ and vice versa) to be achieved, whilst each participant only undergoes the treatment once. Randomising the length of the baseline phase for each participant means that any observed effect cannot be better understood as a function of time elapsed since the baseline assessment or other research procedure. The minimum number of participants required for an MBD study is two, although three or more is typical⁴². Thus, this project will use a sample size of four participants per study, to mitigate against any potential drop out or high levels of missing data.

11.3. Analysis Populations

All participants recruited to the study will be documented fully with respect to receiving the intervention and participating in follow up. Adverse events will be reported for all participants.

11.4. Decision points and stopping rules

There are no interim analyses or formal stopping rules in relation to this study given the small sample size and its exploratory nature.

11.5. The Level of Statistical Significance

This is not applicable: no significance testing will be undertaken given the small sample size and exploratory nature of the study.

11.6. Procedure for Accounting for Missing, Unused, and Spurious Data.

There will be no statistical methods applied for handling missing data as this approach is inconsistent with the single experimental case design. For each participant, phases with fewer than five datapoints will be omitted from analysis, since this is the minimum recommended for within-phase analyses⁴⁰.

12. DATA MANAGEMENT

The plan for the data management of the study is outlined below. There is not a separate Data Management document in use.

12.1. Source Data

Source documents are where data are first recorded, and from which participants’ CRF data are obtained. These include, but are not limited to, hospital records (from which current diagnosis and medication levels may be extracted to record in the CRF), and study assessment measures.

All documents will be stored safely in confidential conditions. On all study-specific documents, other than the signed consent, the participant will be referred to by a participant number/code, not by name.

12.2. Access to Data

Direct access will be granted to authorised representatives from the Sponsor, host institution and the regulatory authorities to permit study-related monitoring, audits and inspections.

12.3. Data Recording and Record Keeping

All study data will be entered on paper or electronic CRFs and transcribed or entered directly to the clinical data management system. Data will be anonymised using a unique study ID. Personal data and participant identification codes will be kept separately from the research data. Access to these data will be strictly on a need-to-know basis. Any secure data transfer will take place in accordance with University of Birmingham policies.

Data will be entered from paper CRFs to the clinical database, or recorded directly on eCRFs as soon as possible after the study visit. Validation of all data entered into the clinical database is achieved through manual review. All critical data items are 100% checked against original source documents, where applicable, to ensure accuracy and an error rate is established across all fields to ensure a consistently accurate dataset.

Audio recordings of therapy sessions and feedback will be taken using a password-protected recording device. They will be immediately deleted from the device once they are transferred onto a secure university server. Recordings should be transferred and deleted from the device within one working day of the appointment in which they were made.

Recordings of therapy sessions will be used for the purposes of clinical supervision and treatment development only. These will be downloaded, encrypted, and stored on a secure server. Only a qualified clinical psychologist will have access to this data for the sole purpose of ensuring the quality of the therapy. All audio-recordings will be deleted one year after the end of the study.

Recordings of qualitative feedback will be transcribed by the research team. Transcriptions will be de-identified, and audio files will be deleted after the transcripts have been checked for accuracy by a second researcher. Transcripts will be used along with written qualitative feedback as outlined in section 12, '*Data Analysis*'.

Electronic data will be kept on a secure University of Birmingham server. Hard copy of data will be kept in a locked filing cabinet in a locked University of Birmingham office.

The report of the study will not identify any individuals. Data will be kept for 10 years following publication of the results.

